8.4 Sensitivity Analysis

To evaluate the magnitude of potential bias from including, as matched controls, people who are registered with GP practices but who do not attend their practice, we will also repeat the primary analysis for mental health, healthcare utilisation and work-related outcomes including only matched controls with at least one primary care encounter in the year preceding their index date.

We will also repeat the primary analysis for mental health, healthcare utilisation and work-related outcomes extending the outcome period to four years.

To assess the impact of missing ethnicity data, we will repeat the ethnicity sociodemographic subgroup analysis amending missing ethnicity entries to white.

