4.4 Primary Endpoints

Objective	Endpoints
1	An incident diagnosis of vitiligo is the date of the first diagnosis code in the record and no alternative diagnosis that merits exclusion (other causes of skin hypopigmentation) diagnosed within a one-year period (six months before or after their first vitiligo diagnosis code).

Table 1: Primary endpoints.

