7.1 Inclusion Criteria

People must meet all the following inclusion criteria to be eligible for inclusion in the study:

- The cohort for the endpoint analysis will consist of all adults and adolescents (aged 13+) contributing to OPCR during the study period.

- The cohort for the lifetime risk analysis will consist of all people contributing to OPCRCD during the study period.
- The vitiligo cohort consists of people newly diagnosed with vitiligo at any point during the study period.

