7.3 Matching Process

For objectives 2-5, controls for each vitiligo case will be identified from the pool of people without a vitiligo diagnosis registered in the OPCRCD database at the time of vitiligo diagnosis for the case. Vitiligo cases will be eligible as controls up until the date of their vitiligo diagnosis (at which date their follow-up will be censored if selected as a control).

Each case will be assigned an index date at the time of their vitiligo diagnosis. Corresponding controls assigned to each case will have the same index date.

Each individual with vitiligo will be matched at their index date with up to four unaffected controls. Controls cannot be diagnosed with vitiligo at the date of matching and will require at least one year of follow-up time to minimise the risk of a non-recorded existing diagnosis of vitiligo. Time-updated exact matching will be performed by age, sex, ethnicity and deprivation, selected from the pool of eligible people registered in the same GP practice.

If required, a combination of time-dependent propensity score matching and exact matching will be performed to create a baseline matched dataset.

The matching process is subject to change depending on the feasibility of the mentioned matching process during the initial exploration of the data. The produced baseline matched dataset will be used for all analyses for objective 2-5.

8. Statistical Analysis

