8.2 Primary Endpoint Analysis

Objective 1

Lifetime risk of vitiligo will be calculated for the population as a whole and by sex, ethnicity, and SES. Ethnicity will be grouped using the standardised definitions of major UK ethnic groups: white, black, Asian, mixed, and other.(7) SES will be defined using the national deprivation measure; IMD.(12)

Lifetime risk will be calculated using methods to estimate cumulative lifetime risk recently published in the Lancet,(13, 14) accounting for the competing risk of death. Key outputs will be lifetime risk plots, presenting the cumulative risk of vitiligo against age for the whole population and for sociodemographic subgroups. At a particular age, the cumulative risk estimate can be interpreted as the lifetime risk of vitiligo up until and including the year of age in question. Age of 80 is considered to be the approximate

lifetime expectancy in the UK,(15) and will be the point of comparison at which the lifetime risk of vitiligo will be compared across sociodemographic subgroups.

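### The check for registered non-attenders covers matched controls only, so possible dilution of the primary lifetime-risk estimate goes unassessed

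*Combined protocol and SAP*

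**What the plan says.** Section 8.4 names a possible source of bias: "potential bias from including, as matched controls, people who are registered with GP practices but who do not attend their practice". Its remedy is limited in two ways. On outcomes, "we will also repeat the primary analysis for mental health, healthcare utilisation and work-related outcomes". On people, the repeat is done "including only matched controls with at least one primary care encounter in the year preceding their index date". Section 7.3 fixes where matched controls are used: "The produced baseline matched dataset will be used for all analyses for objective 2-5".

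The primary objective is built differently. Under 7.1, "The cohort for the lifetime risk analysis will consist of all people contributing to OPCRCD during the study period", with no condition on attendance. The event depends on the record (4.4): "An incident diagnosis of vitiligo is the date of the first diagnosis code in the record". Section 8.2 sets the comparison: "Lifetime risk of vitiligo will be calculated for the population as a whole and by sex, ethnicity, and SES", with subgroups compared at age 80.

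The other sensitivity analyses in 8.4 are a four-year outcome window for the matched outcomes and a recode of missing ethnicity. Neither concerns attendance, and the limitations in section 9 do not mention it.

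**The concern.** A diagnosis code requires contact with care. Person-time during which someone is on a practice list but could not be diagnosed there adds to the Objective 1 denominator and can add nothing to the numerator. The clearest case would be a person who has moved away but remains listed.

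The plan thinks non-attendance worth testing in its secondary objectives. It has no corresponding test in the primary one, where such time enters the estimate directly. The subgroup comparison is what is at stake. If undiagnosable time is more common in one ethnic group or deprivation quintile than another, part of any difference in lifetime risk at age 80 would reflect contact with the practice and not vitiligo. Objective 4 itself treats differences in healthcare use across these subgroups as an open question among people with vitiligo, so equal contact cannot simply be assumed.

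**Working it through.** **Inputs.** The plan gives no precision figure for lifetime risk and no attendance rate, so there is no stated figure to reproduce. All shares below are assumptions. From the documents: 8,000 anticipated vitiligo cases (section 6), deprivation quintiles (5.7.2), comparison at age 80 (8.2), and a global prevalence of 0.5-2.0% (3.1), used only as a scale for the true risk.

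**Step 1: effect on one group.** If a share f of person-time cannot yield a recorded diagnosis and the true hazard is the same throughout, recorded hazard = (1 - f) x true hazard. This was carried through to cumulative incidence at age 80 with death as a competing risk (assumed Gompertz mortality, 0.00003 x exp(0.095 x age) per year). With f = 10%, true risks of 0.5%, 1.0% and 2.0% are recorded as 0.450%, 0.900% and 1.802%. The relative loss is close to f.

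**Step 2: effect on a comparison.** Let g1 and g2 be the non-attending shares in two groups with equal true risk, and w the fraction of non-attending time that is undiagnosable. The recorded ratio is about (1 - w g2)/(1 - w g1).

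| Assumed g1 v g2 | w = 1 | w = 0.5 |
|---|---|---|
| 3% v 8% | 0.92/0.97 = 0.948 | 0.96/0.985 = 0.975 |
| 5% v 15% | 0.85/0.95 = 0.895 | 0.925/0.975 = 0.949 |
| 5% v 20% | 0.80/0.95 = 0.842 | 0.90/0.975 = 0.923 |

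With equal shares the ratio is 1.00. The competing-risk calculation gives 0.895 to 0.896 for 5% v 15% (w = 1) across the three true risks, so the approximation is adequate and the ratio hardly depends on the true risk.

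**Step 3: would such a ratio stand out?** Suppose the 8,000 cases split evenly over quintiles: 8,000/5 = 1,600 each. The 95% half-width on the log ratio is 1.96 x sqrt(2/1600) = 0.069, a factor of exp(0.069) = 1.07.
- w = 1: upper limits are about 1.02, 0.96 and 0.90, so the second and third ratios would appear as differences.
- w = 0.5: upper limits are about 1.04, 1.02 and 0.99, so only the third would, and narrowly.

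Ethnic groups will not be equal in size. With an assumed 200 v 6,000 cases the half-width is 1.96 x sqrt(1/200 + 1/6000) = 0.141, a factor of 1.15. A ratio of 0.895 then has an upper limit of about 1.03 and 0.842 one of about 0.97.

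**The case against.** The strongest reply is that the check in 8.4 addresses a problem specific to matching. Every case has a contact that generated the code at the index date, while a control needs none. A registered-population incidence analysis has no such asymmetry, and 8.4 speaks only of a potential bias whose size is to be evaluated. This stands in part: the plan has not conceded a bias in Objective 1, and the extension needs its own argument. The argument is the shared dependence on contact for a code to exist.

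Second, not attending is different from being undiagnosable. A well person who stays away can still present and be coded if vitiligo appears, and late presentation may still fall before age 80. Their time is then valid time at risk. This also stands, and is why the w = 0.5 column is shown.

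Third, the precision illustration is favourable. Section 6 gives 8,000 for the anxiety and depression calculation, lifetime risk covers all ages, and quintiles follow the national distribution, so equal case counts are not given.

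A reader might also infer that lifetime risk is understated overall. The documents do not settle that. Section 7.2 excludes people without vitiligo who have under one year of follow-up. If applied to this cohort, that removes non-case time and pushes the estimate up. It does not answer the present point, because it concerns time in the dataset and a registered non-attender passes it.

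**Conclusion.** The gap is real. A check the plan considers worthwhile for objectives 2-5 has no counterpart for the primary objective, whose estimate also depends on contact with the practice. Nothing in 7.2, 8.4 or section 9 covers it.

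A reader might go further and conclude that the denominator is in fact diluted to a different extent in each subgroup. The documents contain no attendance data, overall or by subgroup, and do not support that. What they support is that dilution is possible, could be unequal, and is not assessed.

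The size is conditional. Equal undiagnosable shares would lower absolute risks and leave ratios unchanged. Under the assumed gaps the spurious ratio is about 0.95 to 0.84 if all non-attending time is undiagnosable, and about 0.97 to 0.92 if half is. Some of these would pass for real differences between large subgroups. The main analysis can stand, but its subgroup comparison should carry this check.

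**What to change.** Add the following to 8.4 for Objective 1:

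- Report, overall and by sex, ethnicity and deprivation quintile, the share of person-time without a recent primary care encounter.
- Repeat lifetime risk, overall and by subgroup, on time-updated active person-time, meaning time within a pre-specified look-back of a recorded encounter. The plan's own one-year interval is a natural choice, with a longer window such as three years as a second version.
- Apply the same rule to cases and non-cases, and do not count the diagnostic visit as the qualifying encounter, so that the restriction does not select on the outcome.
- Keep the registered-population estimate as the main result and read the repeat as an upper-side check. Restricting to attenders can overstate risk. It also drops cases whose diagnostic visit is their first contact in the window, and new registrants' time before a first encounter.

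If subgroup ratios barely move, attendance is a less likely explanation for them. If they move towards 1, the report should say so.

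The cost is encounter dates for all contributors, not only the matched cohort, and one further run of the lifetime-risk code per window.

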5.7.2 Sociodemographic subgroups

Age, sex, deprivation and ethnicity will comprise the sociodemographic factors used for stratification of the outcome measures.

Age will be stratified into four age categories: 13-17 (adolescents), 18-20, 30-49, 50+.

Ethnicity will be grouped using the standardised definitions of major UK ethnic groups: White, Black, Asian, mixed, and others. (7)

Deprivation will be defined using the national deprivation measure; index of multiple deprivation (IMD) and stratified into quintiles of deprivation according to the national distribution. (8) IMD is calculated at the point of data extraction, using patient postcode (practice postcode where patient postcode is not available).

6. Sample Size Calculations

A sample size calculation is only applicable to the incidence of mental health conditions of anxiety and depression in people diagnosed with vitiligo.

Assuming 80% power, a 5% level of statistical significance and a background population prevalence of 15% for anxiety and 10% for depression,(9), our anticipated sample size for vitiligo (n = 8,000) will be sufficient to detect a risk difference of 1.11% in anxiety between those with and without vitiligo, and 1.12% difference in depression between those with and without vitiligo. Sample size calculations were performed in OpenEpi,(10) results are presented using methods of Kelsey.(11)

7. Populations to be Analysed

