8.5 Missing Data

These studies will use the missing indicator variable method as missing data are considered likely not to be missing at random, meaning multiple imputation approaches will lack validity.

Patients will need to be excluded from analyses based on a matched design if they have incomplete data in the fields (age, sex) required to run the matching process. In similar studies, the exclusion rate due to incomplete data has been very low. (23, 24)

How missing data is handled will be dependent on exploratory and sensitivity analyses and is subject to change.

9. Study Limitations

Disparities between sociodemographic subgroups will be interpreted based on the assumption of the primary/secondary outcomes being related to the vitiligo. We have no definite way to identify that every occurrence of an outcome is related to vitiligo in the context of healthcare utilisation and work impact outcomes and therefore causal interpretation is not possible.

This is an ecological study limited to the UK population and may not be generalisable to other populations.

We expect some missing data for the ethnicity variable, this is a limitation of the dataset itself and could result in bias. Necessary sensitivity analyses will be undertaken to circumvent this and limit any impact this could have in interpretation of results in our analysis.

We expect low number of occurrences for the outcomes of referrals for adjustment disorder and parasuicide/suicide, thus reporting of the results for these two endpoints will depend on the sufficiency of numbers available.

10. Statistical Software

All statistical analyses will be performed using R version 4.2.3 or higher.

11. Ethics

The study will be conducted in accordance with legal and regulatory requirements, as well as with scientific purpose, value and rigor and follow generally accepted research practices described in:

- Guidelines for Good Pharmacoepidemiology Practices (GPP). Public Policy Committee, International Society of Pharmacoepidemiology. Pharmacoepidemiology and Drug Safety 2016; 25:2-10.
- Good Practices for Outcomes Research issued by the International Society for Pharmacoeconomics and Outcomes Research (ISPOR)
- Good practices for real-world data studies of treatment and/or comparative effectiveness: Recommendations from the joint ISPOR-ISPE Special Task Force on real-world evidence in health care decision making

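### The only named check for missing ethnicity recodes it all to White, so it cannot test the non-White estimates and can distort the ethnic contrast in either direction

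*Combined protocol and SAP*

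**What the plan says.** Ethnicity enters the primary objective directly. Section 8.2 states: "Lifetime risk of vitiligo will be calculated for the population as a whole and by sex, ethnicity, and SES". Subgroups are to be compared at age 80. Section 5.7.2 sets five groups: "White, Black, Asian, mixed, and others".

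Section 9 accepts that the variable will be incomplete: "We expect some missing data for the ethnicity variable, this is a limitation of the dataset itself and could result in bias". It then promises: "Necessary sensitivity analyses will be undertaken to circumvent this and limit any impact this could have in interpretation of results in our analysis". The only such analysis specified is in section 8.4: "we will repeat the ethnicity sociodemographic subgroup analysis amending missing ethnicity entries to white".

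The general approach is in section 8.5: "These studies will use the missing indicator variable method as missing data are considered likely not to be missing at random". Multiple imputation is set aside for that reason. The same section leaves room for revision, "How missing data is handled will be dependent on exploratory and sensitivity analyses and is subject to change", but names no alternative. No missingness rate, overall or by case status, is given anywhere.

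**The concern.** A sensitivity analysis for missing data should show how far the result could move under plausible alternatives. This one tries a single allocation, and four of the five ethnic groups cannot respond to it. If the recorded Black, Asian, mixed or other risks are biased because ethnicity is recorded more (or less) often in people with a vitiligo diagnosis, the recode returns the same biased values.

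The White estimate, meanwhile, absorbs everyone with unknown ethnicity, whatever their true group. If that pool has a different case proportion from recorded White people, the White risk shifts and the ethnic contrast shifts with it. The contrast at stake is part of the primary objective.

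The scope is also unclear. The other two analyses in section 8.4 are confined to mental health, healthcare utilisation and work outcomes. The ethnicity check does not say whether lifetime risk is included. If it is not, the primary objective has no named check for missing ethnicity.

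**Working it through.** The plan states no figure to reproduce, so every rate below is an assumption. Risk is treated as a simple proportion. The planned estimate is cumulative to age 80 with death as a competing risk, so these figures show direction and rough size only.

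**Inputs (assumed).** White share w = 0.82. True risk r = 0.01 in every group. Ethnicity is missing in a fraction a of cases and b of non-cases, the same in each ethnic group.

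**Formulas.**
- Risk in any group with recorded ethnicity = r(1−a) / [r(1−a) + (1−r)(1−b)]. For the non-White groups this is the same before and after the recode.
- White risk after the recode = C / (C + D), where C = wr + (1−w)ra and D = w(1−r) + (1−w)(1−r)b.

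**Results.**

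| Missing: cases / non-cases | Recorded-group risk | White after recode | Non-White:White before → after |
|---|---|---|---|
| 10% / 20% | 0.009/0.801 = 1.124% | 0.00838/0.85582 = 0.979% | 1.00 → 1.147 |
| 10% / 30% | 0.009/0.702 = 1.282% | 0.00838/0.87364 = 0.959% | 1.00 → 1.337 |
| 20% / 10% | 0.008/0.899 = 0.890% | 0.00856/0.83818 = 1.021% | 1.00 → 0.871 |
| 20% / 20% | 0.008/0.800 = 1.000% | 0.00856/0.856 = 1.000% | 1.00 → 1.000 |

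In the first row every recorded-group risk is 12% too high. The recode takes that inflation out of White only. Varying the White share from 80% to 90% changes little: the first-row ratio stays at 1.14 to 1.15 and the second at 1.31 to 1.34.

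**A true difference can shrink.** Take White risk 1%, non-White 1.5%, and 20% missing in everyone. White after the recode = (0.82×0.01 + 0.18×0.2×0.015) / (0.82 + 0.18×0.2) = 0.00874/0.856 = 1.021%. The ratio falls from 1.50 to 1.5/1.021 = 1.469.

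**How much of the range the plan shows.** If all missing entries went to a pooled non-White group instead, the first row would give a non-White risk of 0.00262/0.34318 = 0.763%, against 1.124% in White: a ratio of 0.68. The second row would give 0.00262/0.42436 = 0.617% against 1.282%: 0.48. The planned check shows one end of 0.68 to 1.15, or of 0.48 to 1.34.

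**Objectives 2-5.** One simulated dataset was run in each of two scenarios (8,000 cases, 32,000 controls, 20% missing ethnicity). The non-White stratified odds ratios were identical to four decimals before and after the recode. The White odds ratio moved from 1.2155 to 1.1525 in one scenario and from 1.2741 to 1.3358 in the other. In a pooled interaction model the non-White odds ratios moved by less than 0.5% (for example 1.1432 to 1.1482), through shared covariates.

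**The case against.** Five points can be made for the plan.

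- **Most people with missing ethnicity may be White.** If so, the recode is close to right. The documents offer nothing to support it, and keeping this scenario as one bound respects the possibility.
- **A missing category would expose the problem.** Under the missing indicator approach in section 8.5, the 10%/20% illustration gives a missing-group risk of 0.001/0.199 = 0.50%, against 1.12% in the recorded groups. That would be a clear warning. It stands as partial mitigation, because the plan does not say that lifetime risk will be reported for a missing category.
- **A moving White estimate is itself a signal.** In the first illustration the main ratio is a correct 1.00, and a shift to 1.15 is discordance that a careful reader would question. This stands. The shift cannot, however, show whether the non-White risks are biased, or by how much.
- **Allocating by recorded mix assumes missing at random, which section 8.5 doubts.** This is correct, and such a scenario must be labelled accordingly. The allocation must also condition on case status. If it does not, the true ratio of 1.50 with 20% missing in everyone is diluted to 1.418%/1.018% = 1.39, worse than the planned recode. Within case status it returns 1.50 in that scenario, and 1.00 in the equal-risk scenarios.
- **Handling is open to change.** It is, but an alternative chosen after seeing the data carries less weight than one stated beforehand.

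A reader might infer that the recode always lowers the White risk, widens the gap, and so would appear to confirm a disparity. The documents do not support this. They give no missingness by case status, and the 0.87 and 1.47 results show shifts the other way. How readers would interpret the result is conjecture.

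**Conclusion.** The concern holds as a limit of the planned check. That stratum-specific non-White estimates cannot move is a matter of structure and needs no assumed rate. A misleading contrast is conditional: the pool with missing ethnicity must differ from recorded White people in risk. With equal true risks and missingness unrelated to case status, nothing happens. Under the assumed rates the equal-risk ratio moves to between 0.87 and 1.34, and a true 1.50 falls to 1.47.

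The plan itself considers the data likely not missing at random, so one one-way scenario is not an adequate check on a primary-objective comparison. It should be supplemented before the analysis is run.

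A reader might also infer that the main ethnicity analysis is wrong. That is not shown: in the equal-risk illustrations the recorded-ethnicity ratio is 1.00 throughout. The numerical demonstration of a spurious difference concerns lifetime risk only. For Objectives 2-5 it is shown that the White estimate moves and the non-White estimates do not.

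**What to change.** Amend section 8.4 as follows.

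1. State that the missing-ethnicity check covers lifetime risk at age 80, and apply it there first.
2. Report the percentage with missing ethnicity in cases and in non-cases, and lifetime risk in the missing-ethnicity category.
3. Keep the all-White scenario, described as one bound.
4. Add a scenario that allocates missing entries by the recorded ethnic mix within case status, practice (or region), sex and age band, labelled as a missing-at-random scenario.
5. Add an opposite bound: a stated share of missing entries, larger than the recorded non-White share, goes to the four non-White groups in proportion to their recorded sizes.
6. For Objectives 2-5, apply the scenarios only where matched sets can be kept or rebuilt. Section 7.3 plans that "Time-updated exact matching will be performed by age, sex, ethnicity and deprivation", while section 8.5 lists only age and sex as fields needed for matching. The plan should say how cases with missing ethnicity are matched.

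The cost is SAP wording and a few re-runs on existing data. The bounds will be wide if missingness is high, and Objectives 2-5 may need rematching.
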